6.2 Endpoints

Clinical study endpoints and associated definitions are listed in Table 3.

Table 3. COSTA clinical study endpoint definitions.

Endpoints	Definitions	
Primary	To evaluate the safety and tolerability of alvelestat administered twice daily (bid) for 5 or 10 days	
By treatment group (alvelestat/placebo):
 
 • Numbers and % of subjects who experience at least 1 treatment-emergent adverse event to Day 60 (Safety Outcome Assessment) • Adverse events of special interest (liver function abnormalities, corrected QT interval, infections, and neutropenia) and clinically significant safety monitoring labs tests to EoT • Number and % of subjects that discontinue alvelestat to Day 5 or 10 • Number and % of subjects requiring dose reduction to Day 5 or 10 • Number and % of subjects with AE of headache on prospective questioning and CTCAE severity Grade to Day 5 or 10 • Change in vital signs, EKG, safety laboratory measures to Day 5 or 10 or EOT
Secondary	To evaluate the effect of alvelestat on blood pharmacodynamic markers of Neutrophil Extracellular Trap (NET) activation, elastase, inflammatory and coagulopathy activity	
By treatment group (alvelestat/placebo), change from baseline to Day 5 or 10 in:
 
 • Blood biomarkers of NETosis (cell-free DNA; citrullinated histone H3; Myeloperoxidase (MPO)-DNA complexes) • Blood biomarkers of inflammation (absolute neutrophil count; absolute lymphocyte count; neutrophil-lymphocyte ratio [NLR], C-Reactive protein, procalcitonin) • Pro-inflammatory cytokines IL-1beta, IL-6, IL-8, TNF-alpha) • Coagulopathy as measured by D-Dimer • Plasma desmosine/isodesmosine
	To explore the effect of alvelestat on pulmonary function	
By treatment group (alvelestat/placebo):
 
Proportion of subjects alive and free of respiratory failure (without need for non-invasive or invasive mechanical ventilation, high flow oxygen, or Extracorporeal Membrane Oxygenation (ECMO) at Day 29

	The effect of alvelestat on clinical outcomes	
By treatment group (alvelestat/placebo):
 
 • Mortality rate at Day 90 • Proportion of subjects alive and free of respiratory failure (without need for non-invasive or invasive mechanical

Endpoints	Definitions

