- In analyses of oxygen need, patients in ventilator care (non-invasive or invasive mechanical) will be considered in oxygen need for the corresponding time period and patients with death as outcome will be considered in oxygen need for the remainder of the time period of evaluation.
- In analyses of non-invasive ventilator need, patients that require invasive mechanical ventilation will be considered also as having a non-invasive ventilator need. Patients with death as an outcome will be considered as having non-invasive ventilator need from time of death for the remainder of the time period of evaluation.

- In analyses of invasive mechanical ventilator need, patients with death as an outcome will be considered in invasive mechanical ventilator need for the remainder of the time period of evaluation
- The change from baseline in the WHO ordinal scale will use the baseline score and the score at the endpoint using imputation for missing data as stated above, that is the last assessment of their status prior to this time point will be used.
- If the patient is discharged and no further hospitalization data are available, then the patient will be assumed to not have been readmitted. Thus, no additional imputed days on hospitalization will be added to the number of days recorded on available assessments for these patients.

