- Change from baseline in desmosine/isodesmosine will be compared between treatments using ANCOVA models with treatment allocation as a factor and baseline desmosine/isodesmosine as a covariate. Estimated treatment difference with 95% confidence intervals and associated 2-sided p-value will be given.
- Biomarker values that are below the lower limit of quantitation of assay will be reported as the lower limit of quantitation (LLQ)/2.
- Biomarker values may be log transformed if appropriate.

The proportion of patients with recovery at Day 29 will be compared between treatment groups using a logistic regression model adjusting for treatment and COVID disease severity. The difference between treatment arms will be expressed as a difference in proportions as measured by the Cochran Mantel-Haenzel (stratum)-weighted estimator based on the fitted logistic regression model. The delta method will be used to calculate the standard error for the difference and the associated confidence interval [Ge, 2011]. In addition, the raw proportions per treatment group will be given. If 0 events in any of the groups only raw proportions will be given.

Summaries of the results of the secondary analysis for recovery are displayed in Table 10.

Table 10. COSTA analysis tables – Secondary Analysis (Recovery)

Table #	Table Name	Table Contents
	Proportion of Patients with Recovery at 29 Days, ITT	Overall and by Treatment Group 
 • By Age Group • By Sex • By COVID Disease Severity
	Proportion of Patients with Recovery at 29 Days, PP	Overall and by Treatment Group

Patients that die in the study will be handled as worst case in all analyses.

To have an evaluation using all patients we will count an event as the type of need or worse (e.g., patients with oxygen need; non-invasive ventilator need; ventilator need; or with death at time of evaluation will be counted as having data supporting oxygen need), and included in both denominator and numerator.

8.4.1 Time to a recovery state (Day 1 - Day 29; measured in days)

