8.4.2 Proportion of patients endpoint analyses

Secondary endpoints assessing proportion of patients fulfilling an event will be compared between treatments using a logistic regression model adjusting for treatment. The difference between treatment arms will be expressed as a difference in proportions as measured by the Cochran Mantel-Haenzel (stratum)-weighted estimator based on the fitted logistic regression model. The delta method will be used to calculate the standard error for the difference and the associated confidence interval. For endpoints with a low number of events, the baseline disease state will be dropped from the model. In addition, the raw proportions per treatment group will be given. If 0 events in any of the groups only raw proportions will be given.

- Proportion of patients who are in a recovery state (Days 29 and 60).
- Proportion of patients with improvement of one category using the WHO ordinal scale (Days 10 and 29).
- Proportion of patients with improvement of two categories using the WHO ordinal scale (Days 10 and 29).
- Proportion of patients in use of oxygen (Days 10 and 29).
- Proportion of patients alive and not in respiratory failure (invasive mechanical ventilation or ECMO (Days 10 and 29).
- Proportion of patients receiving non-invasive ventilation (Days 10 and 29).
- All-cause mortality

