8.4.6 Duration of hospitalization (Day 1 - Day 29; measured in days)

The total number of days with recorded use will be the sum of all reported days, regardless of whether the days occur consecutively or in disjoint intervals. Results will be summarized by descriptive statistics including medians and quartiles by treatment arm and compared between treatment groups using Wilcoxon rank sum test.

Summaries of the results of the secondary analyses are displayed in Table 11.

Table 11. COSTA analysis tables - Secondary Analyses.

Table #	Table Name	Table Contents
	Time to recovery, Day 1 - Day 29	Overall and by Treatment group
	Proportion of patients in recovery at Day 60, ITT	Overall and by Treatment group Day 1 – Day 10 Day 1 – Day 60
	Proportion of patients with improvement of one category using the WHO ordinal scale from Day 1, ITT	Overall and by Treatment group Day 1 – Day 10 Day 1 – Day 29
	Proportion of patients with improvement of two categories using the WHO ordinal scale from Day 1, ITT	Overall and by Treatment group Day 1 – Day 10 Day 1 – Day 29
	All-cause mortality, ITT	Overall and by Treatment group At Day 29 At Day 60

Table #	Table Name	Table Contents
	Proportion of patients alive and not in respiratory failure (invasive mechanical ventilation or extracorporeal membrane oxygenation (ECMO) at Day 29, ITT	At Day 90 Overall and by Treatment group Day 1 – Day 10 Day 1 – Day 29
	Summary of the proportion of patients re-hospitalized following initiation of study medication and subsequent discharge (over 60 days), ITT	Overall and by Treatment group
	Duration of hospitalization from Day 1 (Day 1 - Day 29; measured in days), ITT	Overall and by Treatment group
	Change from baseline WHO ordinal scale at Days 10 and 29, ITT	Overall and by Treatment group Baseline – Day 10 Baseline – Day 29
	Total time on supplemental oxygen (Day 1 - Day 29; measured in days), ITT	Overall and by Treatment group
	Total time of non-invasive ventilation or high flow oxygen use (post-dose Day 1 - Day 29; measured in days).	Overall and by Treatment group
	Summary of the proportion of patients with oxygen use at Days 10 and 29, ITT	Overall and by Treatment group
	Summary of the proportion of patients with non-invasive ventilation or high flow oxygen use at Days 10 and 29, ITT	Overall and by Treatment group

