	Proportion of patients receiving invasive mechanical ventilation or extracorporeal membrane oxygenation (ECMO, WHO ordinal scale criteria) at Days 10 and 29, ITT	Overall and by Treatment group Day 1 – Day 10 Day 1 – Day 29

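### SAP 8.4.2 and Table 11 report freedom from respiratory failure on a narrower definition and fewer days than protocol 4.0, 9.3.1 and SAP Table 3; the WHO responder cut-offs also differ.

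*SAP*

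**What the plan says.** **Respiratory failure.** Protocol 4.0 makes being alive without respiratory failure the disease-progression endpoint at Day 29 and a clinical-outcome endpoint at Days 5, 10 and 60. Protocol 9.3.1 counts high-flow oxygen, ECMO, and non-invasive or invasive ventilation as failure. SAP 6.2 (Table 3) agrees: "without need for non-invasive or invasive mechanical ventilation, high flow oxygen, or Extracorporeal Membrane Oxygenation (ECMO) at Day 29", with Days 5, 10 and 60 listed under clinical outcomes.

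SAP section 8 departs from this. Section 8.4.2 lists "Proportion of patients alive and not in respiratory failure (invasive mechanical ventilation or ECMO (Days 10 and 29", and Table 11 has the row "Proportion of patients alive and not in respiratory failure (invasive mechanical ventilation or extracorporeal membrane oxygenation (ECMO) at Day 29, ITT", whose contents cover Days 10 and 29. Table 11 also has a separate row, "Proportion of patients receiving invasive mechanical ventilation or extracorporeal membrane oxygenation (ECMO, WHO ordinal scale criteria) at Days 10 and 29, ITT", and another, "Summary of the proportion of patients with non-invasive ventilation or high flow oxygen use at Days 10 and 29, ITT". The 8.4.2 bullet matching that last row is shorter: "Proportion of patients receiving non-invasive ventilation (Days 10 and 29".

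**WHO responders.** Protocol 4.0 and SAP Table 3 specify improvement and deterioration by more than 1 and more than 2 points at Days 5, 10, 29 and 60. SAP 8.4.2 and Table 11 analyse improvement of one and of two categories at Days 10 and 29 only.

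**Other secondary endpoints.** Protocol 10.3.2 plans absolute and percentage change in SaO2/FiO2, descriptive statistics for ICU stay, and Kaplan-Meier with log-rank for time to room air. SAP section 8 has no method or table for any of the three. SAP 7.4 says that time to recovery is the only time-to-event analysis.

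**The concern.** Section 8 is what the programmer will follow. Followed literally, it publishes a different event under the name of a defined endpoint, and the defined endpoint gets no row. The WHO response has the same difficulty: two cut-off schemes are in force, and nothing says which governs. With 5 to 10 patients per arm, one reclassified patient visibly changes a proportion. If the choice of definition is left until after unblinding, it can no longer be shown to be independent of the results.

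**Working it through.** The plan gives no figure to reproduce here, so the check maps each definition onto the WHO scale (0 to 8).

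**1. Which scores count as success**
- Protocol 9.3.1 and SAP Table 3: alive, with no high-flow oxygen, non-invasive or invasive ventilation, or ECMO. That is scores 0 to 4.
- SAP 8.4.2 and Table 11: alive, with no invasive ventilation or ECMO. That is scores 0 to 5.
- Only score 5 (non-invasive ventilation or high-flow oxygen) changes class. Protocol 6.1 admits scores 3 to 5, so a patient who enters at 5 and stays there is classified in opposite ways.

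**2. Weight of one patient at score 5 (100/n)**
- Protocol, 15 at 2:1: 100/10 = 10 points; 100/5 = 20 points.
- SAP Table 1, 7 to 8 per arm: 100/8 = 12.5 points; 100/7 = 14.3 points.

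**3. What the Table 11 rows contain**
- Row for alive and not in respiratory failure: share at 0 to 5.
- Row for invasive ventilation or ECMO: SAP 7.4 says "patients with death as an outcome will be considered in invasive mechanical ventilator need for the remainder of the time period of evaluation", so this is the share at 6 to 8. The two rows sum to 100%, so they carry the same information.
- Row for non-invasive ventilation or high-flow oxygen: SAP 8.4 says "we will count an event as the type of need or worse", so this is the share at 5 to 8. Subtracting it from 100% gives the share at 0 to 4, which approximates the Table 3 endpoint at Days 10 and 29.

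Illustration with assumed counts for an arm of 10 (seven at 0 to 4, two at 5, one at 6 to 8): the first row reads 9/10 = 90%, the second 1/10 = 10%, the third 3/10 = 30%, and the Table 3 endpoint is 7/10 = 70%. The counts show the arithmetic and are not a forecast for any visit.

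**4. Days.** Respiratory failure and WHO improvement are each analysed on 2 of the 4 specified days (10 and 29; not 5 and 60). The more-than-1 and more-than-2 deterioration responder is analysed on none.

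**5. WHO cut-offs.** The scale is integer, so more than 1 means at least 2, and more than 2 means at least 3. Scores that qualify:

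| Entry score | Change | At least 1 | More than 1 | More than 2 |
|---|---|---|---|---|
| 3 | Improve | 0–2 | 0–1 | 0 |
| 4 | Improve | 0–3 | 0–2 | 0–1 |
| 5 | Improve | 0–4 | 0–3 | 0–2 |
| 3 | Deteriorate | 4–8 | 5–8 | 6–8 |
| 4 | Deteriorate | 5–8 | 6–8 | 7–8 |
| 5 | Deteriorate | 6–8 | 7–8 | 8 |

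If 8.4.2 means at least one and at least two categories, its upper cut-off equals Table 3's lower one, and Table 3's upper one has no counterpart. The choice has consequences. From entry score 5, intubation (6) is a deterioration only under at least 1, and more than 2 means death alone. From entry score 3, improvement by more than 2 requires score 0.

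**The case against.** The strongest reply is that little is lost. Table 3 is the SAP's own list of endpoint definitions. The broader event can be approximated from another Table 11 row. Protocol 10.3.2 already states summaries or methods for SaO2/FiO2, ICU stay and time to room air, and SAP section 10 allows extra tables. Everything is exploratory in an unpowered pilot of 15. These points set the severity. They do not remove the contradiction: the SAP never says the endpoint is to be derived from that other row, the derivation stops at Days 10 and 29, and the row carrying the endpoint's name would still show a different event.

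A reader might also infer more than the documents support:
- *No later WHO-based analysis and no analysis of worsening.* Recovery is analysed at Day 60, and SAP 6.1 and 7.4 tie discharge and recovery to scores 1 and 2. Section 8.4.2.1 summarises new oxygen use and new non-invasive ventilation or high-flow use to Day 29. These cover part of the ground, though they are not the specified responders.
- *Days 5 and 60 dropped from section 8 altogether.* Biomarkers use Day 5; recovery, mortality and re-hospitalisation use Day 60. The gap concerns respiratory failure and the WHO responders.
- *SaO2/FiO2 deliberately removed.* SAP 5.2 keeps oxygenation as an objective, and the missing Table 3 entry may be a loss in reading the PDF. The gap in section 8 does not depend on that table.
- *SAP Table 2 as a third conflicting cut-off.* It defines improvement and worsening in general terms (at least one point) and need not contradict graded responder cut-offs.
- *A bias towards alvelestat.* The narrower rule applies to both arms, and the documents give no basis for a direction.

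**Conclusion.** The contradiction on respiratory failure is established by the text, and so is the mismatch in WHO cut-offs between Table 3 and 8.4.2. Both should be fixed before database lock. The size of the first depends on how many patients are alive at score 5 on the assessment day, which the documents do not give. With none, there is no difference; an assumed share of 0 to 40% would raise the reported success proportion by 0 to 40 points over the Table 3 endpoint. Protocol 5.4 cites a mean hospital stay of 5 days, so the number at Day 29 may well be small. For the WHO cut-offs, the documents do not settle which inequalities were intended.

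The remaining gaps are minor: no responder analyses at Days 5 and 60, no specified deterioration responder on any day, and no section 8 entry for SaO2/FiO2, ICU stay or time to room air. The primary safety endpoint is untouched.

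**What to change.** Before database lock:
1. In SAP 8.4.2 and Table 11, define success as in Table 3 (WHO 0 to 4) at Days 5, 10, 29 and 60. Report invasive ventilation or ECMO only under its own name, in the Table 11 row that already exists.
2. Confirm which WHO inequalities are intended and write them identically in the protocol endpoint, SAP Table 3, 8.4.2 and Table 11. Plan improvement and deterioration responders at all four days.
3. Carry the protocol 10.3.2 analyses of SaO2/FiO2, ICU stay and time to room air into section 8. Correct the 7.4 sentence on time-to-event analyses, which is already at odds with the time-to-composite-event analysis in 8.3.

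The cost is SAP wording and a few tables. No new data are needed: the schedule has the WHO score at Days 5, 10, 29 and 60 and SaO2/FiO2 on treatment days, and protocol 5.1 and 9.3 collect respiratory support and ICU dates. If at least 1 and at least 2 prove to be the intent, the protocol's endpoint wording needs the same correction.

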8.4.2.1 Sub-sets based on post-randomization outcome

Descriptive summaries of the proportion of patients as well as the duration of the worsening following initiation of study medication will be provided for these endpoints:

- Proportion of patients needing re-hospitalization (post-dose Day 1 – Day 60).
 - Applies to the sub-set of patients that were randomized, treated with study medication and discharged from the hospital alive then re-admitted to the hospital for COVID-19 related treatment.
- Proportion of patients and duration of new oxygen use (post-dose Day 1 - Day 29; measured in days).
 - Applies to the sub-set of patients that were randomized and treated with study medication but then had a new need for supplemental oxygen (score worsened to 4, 5 or 6).
 - Or those which improved during hospitalization (to 3) and then their clinical status worsened again (to 4, 5 or 6).
- Proportion of patients and duration of new non-invasive ventilation or high flow oxygen use (post-dose Day 1 - Day 29; measured in days).

- Applies to the sub-set of alive patients that were randomized and treated with study medication but then had a new need for non-invasive ventilation or high-flow oxygen use (score worsened to 5 or 6).
- Or those which improved during hospitalization (to 3 or 4) and then their clinical status worsened again (to 5 or 6)

The total number of days with recorded use will be the sum of all reported days, regardless of whether the days occur consecutively or in disjoint intervals.

8.4.3 Change from baseline in WHO ordinal scale (Days 10 and 29).

Change from baseline in WHO ordinal scale will be compared between treatments using ANCOVA models with treatment allocation as a factor and baseline WHO score as a covariate. Estimated treatment difference with 95% confidence intervals and associated 2-sided p-value will be given.

8.4.4 Total time on supplemental oxygen (Day 1 - Day 29; measured in days).

The total number of days with recorded use will be the sum of all reported days, regardless of whether the days occur consecutively or in disjoint intervals. Results will be summarized by descriptive statistics including medians and quartiles by treatment arm and compared between treatment groups using Wilcoxon rank sum test. Patients that do not reach the specified score on any day will be counted as 0 days.

8.4.5 Total time on non-invasive ventilator use (Day 1 - Day 29; measured in days).

The total number of days with recorded use will be the sum of all reported days, regardless of whether the days occur consecutively or in disjoint intervals. Results will be summarized by descriptive statistics including medians and quartiles by treatment arm and compared between treatment groups using Wilcoxon rank sum test. Patients that do not reach the specified score on any day will be counted as 0 days.

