5.3.1 Inclusion Criteria

- Male or Female
- Age ≥ 18 years
- Proven SARS-CoV-2 infection (confirmed by PCR from a nasopharyngeal or lower respiratory tract sample)
- A score of Grade 3 to 5 on the WHO 9-point Ordinal Scale
- Male participants must agree to use a highly effective contraception
- Female participants are eligible to participate if not pregnant; not breastfeeding; and at least one of the following conditions is met:
 - Not a woman of childbearing potential
 - OR
 - A woman of childbearing potential who agrees to follow the contraceptive

guidance during the treatment phase and for at least 4 days after the last dose of study medication

- Capable of giving signed informed consent which includes a commitment to comply with the requirements and restrictions listed in the informed consent form (ICF) and within this protocol.

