6 DEFINITIONS

6.1 General

General clinical study definitions are listed in Table 2.

Table 2. COSTA clinical study general definitions.

Term	Definition for Study
Baseline	The most recent pre-dose assessment prior to first dose of study medication.
Clinical status assessment	Each assessment will be recorded as a number in the CRF based on the WHO Ordinal Scale status categories below. Where possible the timing of each assessment should be similar (i.e. morning or evening throughout). The Ordinal Scale is adapted from the WHO R&D Blueprint expert group which measures illness severity over time (https://www.who.int/blueprint/priority-diseases/key-action/COVID19_Treatment_Trial_Design_Master_Protocol_synopsis_Final_18022020.pdf) according to the following criteria: 
 0. Uninfected, no clinical or virological evidence of infection 1. Ambulatory, no limitation of activities 2. Ambulatory, limitation of activities 3. Hospitalized – mild disease, no oxygen therapy* 4. Hospitalized – mild disease, oxygen by mask or nasal prongs* 5. Hospitalized – severe disease, noninvasive ventilation or high flow oxygen* 6. Hospitalized – severe disease, intubation and mechanical ventilation 7. Hospitalized – severe disease, ventilation and additional organ support – vasopressors, renal replacement therapy, extracorporeal membrane oxygenation 8. Death
COVID disease severity	At baseline/randomization, the categorization of COVID-19 disease severity will be in accordance with the FDA's document: COVID-19: Developing Drugs and Biological Products for Treatment or Prevention Guidance for Industry (May 2020). 
 Mild disease (meeting all inclusion and no exclusion criteria): Symptoms of mild illness that could include fever, cough, sore throat, malaise, headache, muscle pain, gastrointestinal symptoms, without shortness of breath or dyspnea and no clinical signs indicative of moderate, severe, or critical severity.

Term	Definition for Study

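### SAP 8.4.2.1: the score lists for new oxygen use and new non-invasive ventilation or high-flow use stop at 6 and leave out WHO score 7, in conflict with SAP 7.4 and 8.4

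*SAP*

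**What the plan says.** SAP 8.4.2.1 plans two descriptive summaries, each giving a proportion and a duration from Day 1 to Day 29.

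- **New oxygen use.** It covers treated patients who "had a new need for supplemental oxygen (score worsened to 4, 5 or 6", and those who "improved during hospitalization (to 3) and then their clinical status worsened again (to 4, 5 or 6".
- **New non-invasive ventilation or high-flow use.** The item opens with "Applies to the sub-set of alive patients that were randomized and treated with study medication" and takes those who "had a new need for non-invasive ventilation or high-flow oxygen use (score worsened to 5 or 6". A second bullet takes those who improved to 3 or 4 and then rose again to 5 or 6.

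Table 2 in SAP 6.1 describes score 7 as "severe disease, ventilation and additional organ support", one step worse than 6 (intubation and mechanical ventilation) and one step short of death at 8. Patients enter with "A score of Grade 3 to 5 on the WHO 9-point Ordinal Scale".

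Two other parts of the SAP set counting rules for the same kinds of need. SAP 7.4 states that "patients in ventilator care (non-invasive or invasive mechanical) will be considered in oxygen need for the corresponding time period". It also counts invasive ventilation as non-invasive need, and counts patients who die as in need of both kinds from death onward. The text of SAP 8.4, the parent section of 8.4.2.1, says "we will count an event as the type of need or worse", and its example of oxygen need includes ventilator need and death.

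**The concern.** Both lists in 8.4.2.1 are cumulative. The oxygen list includes 5 and 6, which are heavier support than oxygen by mask or prongs. The non-invasive list includes 6, which is intubation. A cumulative list that takes in 6 but not 7 has a gap at the most severe state short of death, and the SAP gives no reason for it.

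The gap works in one direction only: it can lower the count and the days in these two summaries, and never raise them. The patients affected are those who reach ventilation with organ support. If such patients fall unevenly between arms, these two summaries would understate new support in the arm that has more of them. Arms are small, so one patient is visible in the proportion.

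**Working it through.** The plan states no figure that depends on these lists, so there is none to reproduce. The check applies the lists to illustrative daily score paths and then works out the weight of one patient.

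**Inputs.** Listed scores: 4, 5, 6 for oxygen and 5, 6 for non-invasive or high-flow use (SAP 8.4.2.1). Scale: SAP Table 2. Baseline scores: 3 to 5 (SAP 5.3.1). Arm sizes: 10 and 5 (protocol 5.2), or 7 to 8 each (SAP Table 1).

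**Rule applied.** Need is new only after a score of 3 or less (oxygen) or 4 or less (non-invasive or high-flow). A patient entering at 4 or 5 already receives oxygen or heavier support, and one entering at 5 is already on non-invasive or high-flow support. Neither is a new user of that support without first improving. Days counted are days at a listed score after that point. The 7-day paths are assumptions; the documents give no event rates.

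| Daily scores | Oxygen, as listed | Oxygen, with 7 | Non-invasive/high-flow, as listed | Non-invasive/high-flow, with 7 |
|---|---|---|---|---|
| 3,3,7,7,7,7,7 | no event, 0 days | event, 5 days | no event, 0 days | event, 5 days |
| 4,4,7,7,7,7,7 | not new | not new | no event, 0 days | event, 5 days |
| 3,4,7,7,7,7,7 | event, 1 day | event, 6 days | no event, 0 days | event, 5 days |
| 3,6,7,7,7,7,7 | event, 1 day | event, 6 days | event, 1 day | event, 6 days |
| 4,6,7,7,7,7,7 | not new | not new | event, 1 day | event, 6 days |
| 3,6,6,6,6,6,6 | event, 6 days | event, 6 days | event, 6 days | event, 6 days |

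The last row is the control: a patient who stays at 6 is handled correctly. The same gap applies after an in-hospital improvement, when the patient goes from 3 to 7 (oxygen) or from 3 or 4 to 7 (non-invasive or high-flow).

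**Death.** A direct move from 3 to 8 is in neither list, and adding 7 does not change that. SAP 7.4 and 8.4 would count it as oxygen need. For non-invasive or high-flow use, the restriction to living patients excludes it, whereas 7.4 counts need from the time of death. Here the defect is two sections giving different answers.

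**Weight of one reclassified patient.** With the whole arm as denominator, the shift is 100/n percentage points:

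- Protocol, 10:5: 100/10 = 10.0 and 100/5 = 20.0.
- SAP, 7 to 8 per arm: 100/7 = 14.3 and 100/8 = 12.5.

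The 2:1 versus 1:1 disagreement between the documents is a separate matter; here it affects only these weights.

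**The case against.** The strongest reply is that SAP 8.4 already governs. Its need-or-worse rule heads the section, and with 7.4 it would put score 7 and death into the count. On that view the lists are loose drafting and no miscount follows. This stands in part: the result depends on which text the programmer follows. It does not remove the problem. The SAP gives no order of precedence. The 7.4 rules sit under missing data, and an observed score of 7 is not missing. The 8.4 rule speaks of status at the time of evaluation. An explicit score list is the natural thing to code, and if the general rules do govern, the lists contradict them and still need editing.

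A second reply is that respiratory support is recorded daily in hospital (protocol 9.3), so most patients will show a listed score before 7. For them the proportion does not move and only days are lost. This stands. For patients treated to Day 5, however, scheduled WHO scoring afterwards falls at Days 10, 29 and 60, so a recorded jump to 7 is possible if scores are not derived from the daily records.

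A third reply is that a patient scoring 5 or 6 is alive anyway, deaths are tabulated elsewhere, and adding post-death days to observed use would mix imputed with recorded time. This also stands. Deleting the restriction to living patients is one acceptable repair among several.

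A reader might infer that the sickest patients are nowhere counted as having worsened, or that an arm with more organ failure looks better in the report as a whole. The documents do not support that. Table 2 defines worsening as any rise of at least one point. Table 3 has deterioration endpoints on the WHO scale. SAP 8.4.3 analyses change in score, and Table 11 reports mortality and invasive ventilation or ECMO. A reader might also carry the gap into the Wilcoxon comparisons in 8.4.4 and 8.4.5, which refer to a specified score without giving one. Nothing says that the 8.4.2.1 lists apply there.

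**Conclusion.** The point holds for the two summaries in SAP 8.4.2.1. As written, all four score lists leave out score 7. Direct moves to 7 (from 3 for oxygen; from 3 or 4 for non-invasive or high-flow use) are missed, and days at 7 are dropped for patients who are counted. The lists conflict with SAP 7.4 and 8.4, and so does the restriction to living patients in the second item.

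The stakes are modest. Both summaries are descriptive and untested, in an unpowered pilot of 15 patients. The shift of 10 or 20 points (protocol allocation), or 12.5 to 14.3 points (SAP allocation), applies per patient whose event status changes. It assumes the whole arm is treated and forms the denominator. For a patient who first passes through a listed score in that summary the shift is zero, and only the duration is short (1 day instead of 6 in the assumed 3-6-7 path). How many patients would be affected cannot be estimated from the documents.

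**What to change.** In SAP 8.4.2.1, change the oxygen list to scores 4 to 7 in both bullets and the non-invasive or high-flow list to scores 5 to 7 in both bullets.

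Add one sentence on death that is consistent with 7.4 and 8.4: either count it as an event in both summaries, or show it in an adjacent column. If it is counted, reword the restriction to living patients to match. In either case, state that days after death are not added to days of recorded use, so that the duration stays an observed quantity.

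The cost is a few words in one SAP section before database lock. No new data are needed: protocol 9.3 already collects daily respiratory support, organ support and date of death.
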